6.1.2.2 Supportive therapies

Supportive treatment is required to manage severe malaria. Such treatments include but are not limited to blood transfusions, fluid replacement therapy, anticonvulsants (refer to [Section 6.2.2](#)) and glucose transfusions. Supportive treatment for management of severe malaria will be administered as per local treatment guidelines and will be documented as concomitant medication in the study database. A minimum basic standard of supportive treatment will be maintained across all the sites participating in the study.

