6.2.2 Concomitant therapy

Prior medications are defined as drugs taken and stopped prior to the first dose of study medication. In this study, all medication administered or taken by the participants up to 72 hours prior first dose has to be reported as prior medication in the appropriate Case Report Forms.

Severe malaria is a multisystem disease and requires treatment for the various signs and symptoms that occur. These will be treated according to the local clinical practice but should not include the administration of additional antimalarials unless the participant meets the criteria for rescue medication. The following medications are recommended for commonly observed symptoms:

- Paracetamol < 3g/day (or equivalent pediatric dosage; 10 to 15 mg/kg orally every 4 to 6 hours) may be used however, exact doses and time should be recorded appropriately.
- Metopimazine for repeated vomiting (or if not available, any other antiemetic which is not known to prolong QT and/or cause torsade de pointes)
- Beta-lactam antibiotics would be preferred in case of a bacterial infection (with the exception of amoxicillin-clavulanic acid because of its potential hepatotoxicity). If needed clindamycin can be given. All other antibiotics, new-quinolones included, should be avoided where possible.
- Lorazepam and furosemide. Diazepam should be allowed only when the suggested alternative lorazepam would not be available.
- Supportive therapy (e.g. blood or glucose transfusion, refer Study Manual)

Each concomitant drug must be individually assessed against all exclusion criteria/prohibited medication. If in doubt, the investigator should contact the Novartis medical/ monitor before randomizing a participant or allowing a new medication to be started. If the participant is already enrolled, Novartis should be contacted to determine if the participant should continue participation in the study, if the time permits based on participant condition.

All medications, procedures, and significant non-drug therapies (including physical therapy and blood transfusions) administered after the participant was enrolled into the study must be recorded on the appropriate Case Report Forms.

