10.2.3 Special Hematology monitoring

Hematology parameters are closely monitored throughout the study to detect early and delayed hemolytic anemia.

Early Hemolytic anemia is defined as 10% or greater decrease in hemoglobin levels and an increase of LDH levels to $>390 \text{ U/L}$, or an increase of $\geq 10\%$ above baseline occurring up to Day 8 of the study.

Delayed hemolytic anemia might occur > 7 days after initiation of parenteral study drug (IV artesunate or IV cipargamin) during the study period. The event is characterized by a 10% or

greater decrease in hemoglobin levels accompanied by increase of LDH levels to >390 U/L, or an increase of $\geq 10\%$ compared to the values measured at Day 8 of the study.

Decrease in hemoglobin 10% or greater (compared to baseline up to Day 8 and compared to Day 8 values after until the end of study), must be always followed by LDH measurement for confirmation of hemolysis and requires close observation, follow-up monitoring and contributing factors are to be recorded on the appropriate CRFs.

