2.1.1 General definitions

Study treatment: IV Cipargamin and IV artesunate are randomized treatments. Coartem tablets (20/120 mg and 80/480 mg tablets) are used for oral therapy following the IV therapy for all patients. Coartem is not an investigational treatment and will not be presented in the treatment group name. Treatment group name will be used in statistical analyses and outputs. These treatment groups will be used as the column headers in the CSR outputs.

For example, the initial treatment groups in Cohort 1-2 will be displayed as:

- IV Cipargamin 20mg

- IV Cipargamin 40mg
- IV Artesunate

As per study design, other IV cipargamin dose levels may also be used. Treatment groups for each of the combinations will be used accordingly. For Cohorts 3 to 5, the IV Cipargamin dose level will be the equivalent dose level intended for patients ≥ 35 kg.

Baseline: The last measurement made prior to administration of the first dose of study treatment. Note: this may include measurements taken on the day of randomization (e.g. lab, ECG, vitals).

Study day: Study day will be calculated with respect to the first dose of study treatment. If a patient did not receive any dose of study treatment then the randomization date will be used as the date of first dose of study treatment. The first day of administration of study treatment (first dose) is defined as Day 1. Day -1 will be the day before Day 1. Day 0 does not exist. For some variables, assessments are collected more than once a day during first 3 days. Study day calculation for such assessments is based on the treatment start date and time.

For the assessments that are performed more than once a day: Study day = Integer (datetime of assessment – datetime of first dose of study treatment)/(60*60*24) + 1.

For assessments that are performed once for a day: Study day = date of assessment – date of first dose of study treatment + 1.

For assessments collected prior to Day 1, study day = date of assessment - date of first dose of study treatment.

Body temperature: Body temperature is measured using different routes (oral/rectal/tympanic/axillary), which will lead to variations in the readings. Therefore, all the temperature readings will be standardized with respect to tympanic equivalent as follows for the reporting purpose:

Body temperature (oral/tympanic/rectal equivalent) = Axillary temperature + 0.5°C.

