Key signs of Severe Malaria are Altered consciousness, Renal impairment, Acidosis, and Respiratory distress.

Signs of severe malaria

The following signs of severe malaria will be monitored at every visit during the entire study duration.

- **Altered consciousness** – Prostration (inability to sit or drink or breast feed) or GCS < 11 for patients > 5 years / BCS < 3 for patients ≤ 5 years of age
- **Renal Impairment** - Serum creatinine > 3xULN or > 3 mg/dL or need for renal replacement therapy (RRT)
- **Acidosis** - Plasma lactate > 4 mmol/L or Respiratory distress.
Respiratory distress is defined as rapid, deep and labored breathing (costal indrawing, use of accessory muscles and nasal flaring)- present or absent.
In database, Plasma lactate is captured under lactic acid.
- **Severe anemia** - Hb < 5 g/dl or Hb < 7g/dl in pediatric and adults respectively or need of blood transfusion
- **Jaundice** - Serum bilirubin > 3 mg/dl
- **Hypoglycemia**- plasma glucose < 40 mg/dL
- **Blantyre coma scale (BCS)** is a number from 0 to 5 based on [Appendix 5, Table 5-1](#) for patients ≤ 5 years. The score is determined by adding the results from three categories: Motor response, verbal response, and eye movement. The minimum score is 0 which indicates poor results while the maximum is 5 indicating good results.

- **Glasgow Coma Scale (GCS)** is a clinical scale used to reliably measure a person's level of consciousness for age > 5 years. The score is determined by adding the results from three categories: Motor response, verbal response, and eye movement. A person's GCS score can range from 3 (completely unresponsive) to 15 (responsive) based on [Appendix 5, Table 5-2](#).

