(ALT or AST) & TBL & ALP	ALT or AST >3xULN & TBL >2xULN & ALP <2xULN

Peak ALT and AST and peak TBL will be plotted using eDISH (evaluation of Drug Induced Serious Hepatotoxicity) method and Modified eDISH (mDISH) method, see Lin, et. al. (2012).

Listing of patients with the following laboratories will be provided:

- Serum creatinine increase 25 – 49% compared to baseline
- Serum creatinine increase $\geq 50\%$ compared to baseline
- New Plasma lactate > 4 mmol/l
- New dipstick proteinuria $\geq 1+$
- New dipstick hematuria $\geq 1+$

For urinalysis, frequency tables will be presented. Number and percent of patients in each category will be presented for each visit.

Laboratory measurements, which are recorded as below the assay detection limits, will be imputed as half of the detection limit; and those above the detection limit will be imputed as within the detection limit, for the summary statistics.

Analysis of Hemolysis

Early Hemolytic anemia is defined as 10% or greater decrease in hemoglobin levels and an increase of LDH levels to >390 U/L, or an increase of $\geq 10\%$ above baseline occurring up to Day 8 of the study.

Delayed hemolytic anemia occurs > 7 days after initiation of parenteral study drug (IV artesunate or IV cipargamin) during the study period. It is defined as 10% or greater decrease in hemoglobin levels and an increase of LDH levels to >390 U/L, or an increase of $\geq 10\%$ above Day 8 value. If Day 8 value is missing, use the closest value.

The number (and proportion) of patients with early hemolysis and number (and proportion) of patients with delayed hemolysis will be summarized by phase (Early or Delayed) and visit (Early: Days 1 to 3, Days 4 to 8, Days 1 to 8; Delayed: Days 9 to 15, Days ≥ 16 , \geq Day 9), cohort, and treatment group. For delayed hemolysis, visits after Day 8 will be reported.

Besides, number and percent of patients with decrease in hemoglobin $\geq 10\%$ (from baseline for early and from Day 8 for delayed) will be summarized by phase (Early or Delayed) and visit, cohort, and treatment group.

Analysis of Lactate

A shift table presenting a shift in lactate levels from baseline to each post-baseline visit will be provided by visit, cohort, and treatment group. The following categories will be used; ≤ 2 , > 2 - <4 , ≥ 4 mmol/l.

The percentage change from baseline in lactate level will be summarized by visit, cohort, and treatment group.

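### The haemolysis definitions ignore transfusion: an early event can be missed in a participant transfused after the first dose, and the delayed count can be pushed either way

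*SAP*

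**What the plan says.** **Definitions.** SAP 2.8.2 gives the early rule as: "Early Hemolytic anemia is defined as 10% or greater decrease in hemoglobin levels and an increase of LDH levels to" above 390 U/L, or an LDH rise of at least 10% over baseline, up to Day 8. Delayed haemolysis needs the same haemoglobin fall with an LDH criterion, measured against Day 8. Protocol 10.2.3 sets the haemoglobin references as "compared to baseline up to Day 8 and compared to Day 8 values after until the end of study". SAP 2.1.1 defines baseline as "The last measurement made prior to administration of the first dose of study treatment". For a missing Day 8 reference the SAP says: "If Day 8 value is missing, use the closest value".

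**LDH.** Under protocol 10.2.3, a haemoglobin fall of at least 10% "must be always followed by LDH measurement for confirmation of hemolysis". Footnote 9 to protocol Tables 8-1 and 8-2 has LDH drawn at pre-dose and Day 8, but analysed only when haemoglobin is down by at least 10%.

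**Transfusion.** On supportive care, protocol 6.1.2.2 says: "Such treatments include but are not limited to blood transfusions". Protocol 6.2.2 covers the recording of non-drug therapies ("including physical therapy and blood transfusions) administered after the participant was enrolled into the study must be recorded"). The severe-anaemia sign in SAP 2.1.1 includes the alternative "or need of blood transfusion". Neither haemolysis definition has such a term, and no other section resets the reference, censors, or counts a transfusion for this endpoint. The additional SAP summary of haemoglobin falls of at least 10% has the same gap.

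**The concern.** Severe anaemia is one of the qualifying signs for Cohorts 2-5 (protocol 16.4), so some participants will probably be transfused early. Their early reference stays at the low pre-dose value, and a later loss of red cells is judged against a level that the transfusion has left well behind. Following the rule as written then returns no event. Because LDH analysis depends on the same haemoglobin trigger, the confirming value may not exist when the data are analysed.

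The risk of haemolysis, early and delayed, is a stated secondary objective. Protocol 4.5 cites delayed haemolysis in 7-27% of severe malaria participants given IV artesunate and says that it might also occur with cipargamin. Transfusion follows local guidelines in an open-label trial, so its use could differ between arms, and the haemolysis comparison would then partly reflect who was transfused.

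**Working it through.** The plan gives no figure for this point that could be reproduced. The check is arithmetic on the rule itself.

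**Inputs**
- Event threshold: 0.9 × reference haemoglobin (protocol 10.2.3, SAP 2.8.2).
- Early reference H0: last pre-dose value (SAP 2.1.1). Delayed reference: Day 8 value.
- Severe-anaemia limits: below 5 g/dL in children under 12, below 7 g/dL in adults (protocol Table 16-6).
- Rise from transfusion, T: not in the documents; assumed 1 to 4 g/dL.

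**Early phase.** The fall from the post-transfusion level needed to qualify is (H0 + T − 0.9 × H0) / (H0 + T). With H0 = 4.5 g/dL (assumed) the threshold is 0.9 × 4.5 = 4.05 g/dL.

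| T (g/dL) | Post-transfusion Hb | Fall needed under the rule | Threshold if reference is reset |
|---|---|---|---|
| 1 | 5.5 | 1.45/5.5 = 26% | 4.95 |
| 2 | 6.5 | 2.45/6.5 = 38% | 5.85 |
| 3 | 7.5 | 3.45/7.5 = 46% | 6.75 |
| 4 | 8.5 | 4.45/8.5 = 52% | 7.65 |

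Over the same range of T, the fall needed is 28% to 55% for H0 = 4.0 and 23% to 46% for H0 = 6.0. As an example, 4.5 is transfused to 7.5 and then falls to 5.5. The loss is 2.0/7.5 = 27%, but 5.5/4.5 is 22% above baseline, so there is no event and no trigger for LDH.

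**Delayed phase, transfused before Day 8.** A value of 5.0 is transfused to 8.0 at Day 8 and is later 7.0. Against Day 8 this is 7.0/8.0 − 1 = −12.5%, so the haemoglobin limb is met, although 7.0 is 40% above the pre-transfusion value. Here the reference is already post-transfusion, and the rule can add events.

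**Delayed phase, transfused after Day 8.** Day 8 is 8.0, haemoglobin falls to 6.0 (−25%), and transfusion brings it to 9.0. If 6.0 was recorded, LDH follows and the event can count. If the next recorded value is 9.0, the change is +12.5% and nothing is counted. A transfusion can also precede a 10% fall: 5.4 to 4.9 crosses the children's limit with a fall of 9.3%. This is possible for references from 5.0 to 5/0.9 = 5.56 g/dL in children and from 7.0 to 7/0.9 = 7.78 g/dL in adults.

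**Which value is used.** SAP Table 5-10 takes the most extreme value in a window for notable abnormalities and the value closest to target for visit summaries. It does not say which applies to haemolysis.

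**The case against.** The strongest reply is that few cases would slip through and that transfusion is visible elsewhere. Haematology is scheduled at 12, 24, 36, 48 and 72 hours and on Days 6, 8, 15, 22 and 29, and also at unscheduled visits. A laboratory abnormality that requires therapy is an adverse event (protocol 10.1.1). The anaemia safety topic includes haemolytic disorders (SAP Table 2-5), the severe-anaemia sign counts transfusion, and non-drug therapies are summarised by arm. The DMC receives the adverse-event, non-drug-therapy and severe-malaria-sign outputs (SAP Table 2-13). All this is right, and it means that an imbalance in transfusion would not be invisible. It does not correct the haemolysis count, which is the endpoint.

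Four stronger readings are tempting, and the documents do not support them:

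- *The rule lowers the haemolysis rate in both arms.* The direction is clear only for the early phase. Day 8 is often already post-transfusion, and then the delayed count can rise.
- *Participants transfused because of haemolysis never get an LDH test.* A 10% fall recorded before the transfusion still triggers one, and liver follow-up also measures LDH (protocol Table 16-2).
- *A known share of each arm cannot be assessed.* Assuming that 10-30% of 116 are transfused gives 12-35 participants, but the share is not in the documents. Only those who also haemolyse after transfusion and stay above 90% of the reference are missed. Nor can the cited 7-27% size the early miss, because it is a delayed rate.
- *The DMC would be misled.* Table 2-13 lists delayed haemolysis only, where the bias has no fixed sign, alongside the outputs named above.

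**Conclusion.** The point holds in limited form. For early haemolysis, the rule as written can return a false negative in a participant transfused after the first dose, and the LDH samples already drawn may then go unanalysed. For delayed haemolysis, transfusion can either mask or add events, depending on whether it comes after or before Day 8. The size per participant is large under the assumed increments (a fall of 26% to 52% in place of 10%, from a baseline of 4.5 g/dL). The number of participants affected cannot be derived from the documents, which give neither the share transfused nor an early haemolysis rate. The endpoint is a descriptive secondary safety endpoint, so no hypothesis, sample size, power or stopping criterion changes. This is a cheap improvement, not a threat to the trial's main conclusions.

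**What to change.** 1. In SAP 2.8.2, keep the current definitions and add a side-by-side count by cohort and arm. When a transfusion falls between the reference and the assessment, the reference becomes the first post-transfusion haemoglobin.
2. Report the number transfused by phase (Days 1-8, after Day 8), and flag transfused participants in the haemolysis tables and in the DMC table.
3. Amend the LDH footnote to protocol Tables 8-1 and 8-2 so that the pre-dose and Day 8 samples already collected are also analysed in participants transfused by Day 8.

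The reset mainly repairs the early count. It does not recover a fall that was transfused before it was recorded, and it leaves a Day 8 value that is already post-transfusion unchanged. The phase counts and flags are there to show those cases.

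The cost is one more derivation from transfusion and serial haemoglobin data that are already collected, a few more LDH assays with no new blood draws, and a short protocol wording change. Some falls from a transient post-transfusion peak may be counted; the LDH limb and the side-by-side layout limit that. SAP 1.1 describes Cohorts 1 and 2 as complete, and the documents do not say whether their unanalysed LDH samples were kept. For those cohorts the added count may have to rest on the haemoglobin limb. The change sets no rule on when to transfuse.

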2.8.3 Other safety data

2.8.3.1 ECG and cardiac imaging data

The following quantitative variables will be summarized for averaged triplicate ECG: heart rate, RR interval, PR interval, QRS interval, QT interval, QTcF (QT interval corrected for heart rate according to Fredericia) and QTcB (QT interval corrected for heart rate according to Bazett) for each timepoint and maximum post baseline value.

Patients with newly notably high QT, HR and fever (≥ 38 °C, tympanic equivalent) will be summarized.

The analysis results for categorical outliers and T-wave morphology may be summarized in frequency tables with counts and percentages for both number of participants and number of timepoints. For categorical outliers, the number of participants (%) and timepoints (and at the maximum post baseline) will be determined by treatment group.

QTc will be summarized categorically by computing the number and percentage of patients at each time point and at the maximum post baseline value with following:

- QT, QTcF, or QTcB
 - > 450 and ≤ 480 ms
 - > 480 and ≤ 500 ms
 - > 500 ms
 - Increase from Baseline of ≥ 30 ms to < 60 ms
 - Increase from Baseline of ≥ 60 ms
- PR
 - Increase from baseline $>25\%$ and to a value > 200 ms
 - > 120 ms
- HR for age ≥ 18 years
 - Decrease from baseline $>25\%$ and to a value < 50 bpm
 - value of <50 bpm
 - Increase from baseline $>25\%$ and to a value > 100 bpm
 - > 100 bpm
- HR for age <18 years
 - $> 90^{\text{th}}$ percentile defined in [Table 2-7](#)
 - $< 10^{\text{th}}$ percentile defined in [Table 2-7](#)
- QRS
 - Increase from baseline $>25\%$ and to a value > 120 ms
 - > 120 ms

For T-wave morphology, if performed, the analysis will be focused on the treatment emergent changes.

Table 2-7 Heart rate cut-offs (beats/minute) based on centile charts

Age Range#	10 th percentile	90 th percentile
Birth	107	148
0 – <3m	123	164
3 – <6m	120	159
6 – <9m	114	152
9 – <12m	109	145
12 – <18m	103	140
18 – <24m	98	135
2 – <3y	92	128
3 – <4y	86	123
4 – <6y	81	117
6 – <8y	74	111
8 – <12y	67	103
12 – <15y	62	96
15 – <18y	58	92

Age ranges given in years (y) and months (m). “Birth” refers to the immediate neonatal period.
Reference: Lancet. 2011 March 19; 377(9770): 1011–1018. doi:10.1016/S0140-6736(10)62226-X.

A line plot by patient (Spaghetti plot) will be provided by visit and treatment group.

In addition, shift tables comparing baseline ECG results (normal, abnormal, not available, total) with the post-baseline results will be provided by visit and at the worst post-baseline result (normal, abnormal, not available, total).

The relationship between change from baseline in QTcF/QTcB and cipargamin plasma concentration will be assessed graphically with change from baseline in QTcF/QTcB plotted against cipargamin plasma concentrations.

Cipargamin plasma concentration-QT relationship may also be explored using linear mixed effects model.

A listing of all newly occurring or worsening abnormalities as compared with baseline will be provided, as well as a by-patient listing of all quantitative ECG parameters.

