All vital signs, body height, body weight, and head circumference data will be listed by cohort, treatment group, participant, and visit/time. If ranges are available, abnormalities (and relevant orthostatic changes) in vital signs will be flagged and listed by cohort, treatment group, participant, and visit/time. Summary statistics will be provided by cohort, treatment group, and visit/time.

12-lead ECG

Abnormal ECG data will be flagged and will be listed by cohort, treatment group, participant and visit/time. Summary statistics may be provided by cohort, treatment group and visit/time.

The analysis results for categorical outliers and T-wave morphology will be summarized in frequency tables with counts and percentages for both number of participants and number of

timepoints. For categorical outliers, the number of participants (%) and timepoints will be determined by treatment group for the following:

- increase in QTcF from baseline of ≥ 30 msec and ≥ 60 msec
- increase in QTcB from baseline of ≥ 30 msec and ≥ 60 msec
- absolute QTcF values > 450 msec, > 480 msec, and > 500 msec
- absolute QTcB values > 450 msec, > 480 msec, and > 500 msec
- PR change from baseline $> 25\%$ increase resulting in PR > 200 msec
- QRS change from baseline $> 25\%$ increase resulting in QRS > 120 msec
- heart rate change from baseline $> 25\%$ decrease resulting in heart rate < 50 beats per minute
- heart rate change from baseline $> 25\%$ increase resulting in a heart rate > 100 beats per minute

For T-wave morphology, the analysis will be focused on the treatment emergent changes.

The relationship between change from baseline in QTcF/QTcB and cipargamin plasma concentration will be assessed graphically with change from baseline in QTcF/QTcB plotted against cipargamin plasma concentrations.

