- for a treatment group in a cohort with 14 patients, the probability of observing at least 2 events is about 80% if the true event rate is $\geq 20\%$ but $< 20\%$ if the true event rate is $\leq 5\%$;
- for a treatment group in a cohort with 20 patients, the probability of observing at least 3 events is about 80% if the true event rate is $\geq 20\%$ but $< 20\%$ if the true event rate is $\leq 7\%$
- for a treatment group in a cohort with 38 patients, the probability of observing at least 6 events is about 80% if the true event rate is $\geq 20\%$ but $< 20\%$ if the true event rate is $\leq 10\%$

- for a regimen that is selected for Cohorts 3-5 with 116 patients, the probability of observing at least 14 events is $> 80\%$ if the true event rate is $\geq 15\%$ but $< 20\%$ if the true event rate is $\leq 9\%$.

The minimal number of events mentioned above may be used as a guidance to interpret the occurrence of safety events in a treatment group in a cohort or pooled cohorts.

Figure 3-3 **Probability of observing selected minimal number of events by sample size**

Generated using R 3.4.3.

4 Change to protocol specified analyses

None

5 Appendix

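### The SAP's stand-alone PR outlier cut-off of 120 ms repeats the QRS value and conflicts with the 200 ms used for PR in its paired rule and in the protocol

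*SAP*

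**What the plan says.** SAP 2.8.3.1 lists ECG outlier categories. Under PR there are two entries: "Increase from baseline $>25\%$ and to a value > 200 ms", and beneath it a value-alone entry at above 120 ms with no baseline or change condition. Under QRS there are also two: "Increase from baseline $>25\%$ and to a value > 120 ms", and a value-alone entry at above 120 ms. For adult heart rate the upper change rule is "Increase from baseline $>25\%$ and to a value > 100 bpm", with a value-alone entry at above 100 bpm; the lower pair uses 50 bpm in both places.

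On how the list is used, the SAP says: "For categorical outliers, the number of participants (%) and timepoints (and at the maximum post baseline) will be determined by treatment group".

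Protocol 12.5.2 has one PR category, a rise of more than 25% from baseline, "increase resulting in PR > 200 msec", and one QRS category, the same size of rise, "increase resulting in QRS > 120 msec". It has no value-alone category for either interval. SAP Section 4, headed "Change to protocol specified analyses", reports none.

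**The concern.** The value-alone PR entry sits 80 ms below the threshold in the PR rule directly above it, and it equals the QRS threshold. That pattern suggests a number carried over from the QRS lines. If it is programmed as written, the PR value-alone row counts values that the SAP's own 200 ms criterion does not regard as prolonged. The table then has no row for absolute PR prolongation, which is the natural purpose of a value-alone entry beside a change-plus-value rule.

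ECG output is scheduled for the interim assessment after Cohort 2 and for the DMC review after Cohort 4 (SAP Table 2-13), so an uninformative PR row could reach those readers too.

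**Working it through.** The documents give no figure to reproduce here. The check is a comparison of the text, followed by a sizing under stated assumptions.

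**1. Thresholds side by side**

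| Parameter | SAP change rule | SAP value-alone | Protocol 12.5.2 change rule |
|---|---|---|---|
| PR | >25% and >200 ms | >120 ms | >25% and >200 ms |
| QRS | >25% and >120 ms | >120 ms | >25% and >120 ms |
| HR, age 18 and over, high | >25% and >100 bpm | >100 bpm | >25% and >100 bpm |
| HR, age 18 and over, low | >25% and <50 bpm | <50 bpm | >25% and <50 bpm |

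Among the SAP parameters that pair a change rule with a value-alone rule in this way, the two thresholds agree for QRS and for both directions of adult heart rate. They disagree only for PR: 200 − 120 = 80 ms. The comparison does not extend to heart rate under 18 years, which uses percentiles without a change rule, or to QT/QTc, where the entries are not paired in this form.

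**2. What the two PR rows capture**

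- Any PR of 121 to 200 ms enters the value-alone row and cannot meet the change rule.
- The change rule needs both a value above 200 ms and a rise of more than 25%. Since 200 / 1.25 = 160, for any baseline of 160 ms or more there are values above 200 ms that fail the rule. From a baseline of 180 ms the value must exceed 180 × 1.25 = 225 ms. A rise from 180 to 220 ms is 40/180 = 22% and fails.
- Such a value appears only in the value-alone row, mixed with everything from 121 to 200 ms. With matched thresholds, subtracting the change row from the value-alone row would give the count above 200 ms without a 25% rise. At 120 ms that subtraction does not work.

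**3. Share of tracings flagged**

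The documents give no PR mean or SD, so both are assumptions. With PR taken as normal with mean m and SD s, the share above c is 1 − Φ((c − m)/s).

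| Assumed mean (ms) | Above 120 ms: SD 15 / 20 / 25 | Above 200 ms: SD 15 / 20 / 25 |
|---|---|---|
| 100 | 0.091 / 0.159 / 0.212 | all <0.0001 |
| 110 | 0.252 / 0.309 / 0.345 | <0.0001 / <0.0001 / 0.0002 |
| 120 | 0.500 / 0.500 / 0.500 | <0.0001 / <0.0001 / 0.0007 |
| 130 | 0.748 / 0.691 / 0.655 | <0.0001 / 0.0002 / 0.0026 |
| 140 | 0.909 / 0.841 / 0.788 | <0.0001 / 0.0013 / 0.0082 |
| 150 | 0.977 / 0.933 / 0.885 | 0.0004 / 0.0062 / 0.0228 |
| 160 | 0.996 / 0.977 / 0.945 | 0.0038 / 0.0228 / 0.0548 |

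At 120 ms the flagged share is 66% to 99.6% for means of 130 to 160 ms, 50% at 120 ms, and 9% to 35% at 100 to 110 ms. At 200 ms it is at most about 5.5% anywhere in the grid. These are shares of single tracings. At the maximum post-baseline value one reading above the cut-off is enough, so the participant-level share is at least as high as at any single time point.

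The age mix affects which row of the table applies: 192 of 252 planned participants (76%) are under 12 years (Protocol Section 5).

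**The case against.** The strongest reply is that little is lost. The PR criterion the protocol planned is reproduced intact in the SAP, and the 120 ms entry is an additional row. PR is also summarised as a continuous variable at each time point and at its post-baseline maximum. SAP 2.8.3.1 adds normal/abnormal shift tables, a listing of new or worsening abnormalities and a by-patient listing of all quantitative ECG parameters. A blinded cardiologist reads all ECGs centrally (Protocol 8.4.5). The SAP says the categorical results may be tabulated, which can be read as optional. The ECG trigger for stopping treatment is QTcF (Protocol 8.4.5), and the recruitment-pause criteria in SAP Table 2-14 do not use PR.

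All of this stands as a limit on the consequence. The optional reading is less secure: the next sentence of the SAP says the counts will be determined, and the protocol says they will be summarised. None of it explains or justifies the 120 ms entry.

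The same facts rule out two stronger readings. A reader might infer that almost every normal tracing would be flagged. The documents give no PR distribution, three quarters of planned participants are under 12 years, and the share falls to 9% to 50% for assumed means of 100 to 120 ms. A reader might also infer that PR above 200 ms without a 25% rise would be counted nowhere. That is true only in the sense that no categorical row isolates it; the continuous summaries and listings would still show it.

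**Conclusion.** The stand-alone PR cut-off is wrong as written and of minor severity. It disagrees with the paired SAP rule and with the protocol's PR threshold, repeats the QRS value, and is not declared as a change. That conclusion, and the misclassification of PR values from 121 to 200 ms, follow from the text alone. That the number was carried over from QRS is the most plausible explanation, but the documents do not prove it.

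The size of the effect rests on the assumed normal distributions and should be quoted only with the full range, 9% to 99.6% across means of 100 to 160 ms. It would be too strong to say that the SAP has dropped the protocol's PR analysis, because that rule is present unchanged.

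**What to change.** In SAP 2.8.3.1, change the value-alone PR entry to above 200 ms, the threshold in the SAP's own change rule and in protocol 12.5.2. Deleting the entry would also be consistent with the protocol, which supplies the 200 ms threshold but has no value-alone PR category. The first option is more useful because it adds a count of absolute prolongation. If 120 ms is intended, record it in SAP Section 4 as an added category and give the reason.

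The cost is one number in the SAP and the matching table shell and program. No new data are needed. It should be settled before database lock and before any further DMC output that uses the category.
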